- 11. Patients with a history of esophageal squamous dysplasia.
- 12. Patient has known carcinoma of the foregut (pancreatic, bile duct, ampullary, stomach, or duodenum) within 5 years prior to study enrollment.

Study procedures:

Participants will report fasting for ≥ 6 hours for the study.

A. Pre-procedure assessment:

- a. Baseline height, weight, hip, and waist circumference will be measured by the research coordinator.
- A validated questionnaire assessing reflux symptoms (RSQ) will be completed by the subject.
- c. At the Mayo Clinic sites only, 10 ml of blood will be obtained via venipuncture for measurement of circulating biomarkers (cytokines, adipokines and methylated DNA markers) of BE risk. Blood will be processed and separated into serum, plasma, and buffy coat for subsequent analysis for BE biomarkers.

Figure 1:25 mm sponge, intact and expanded

- d. Pregnancy test will be obtained for women of child bearing potential.
- B. Capsule sponge assessment:

For phase 1 subjects will be randomized using concealed allocation to one of two capsule sponges: 25 mm 10 ppi, 25 mm 20 ppi. All phase 2 subjects will receive the same single size and porosity sponge (porosity to be determined after analysis of Phase 1).

 Participants will be seated upright and asked to swallow the capsule sponge to which they have been randomized to, with

Figure 2: 30 mm sponge, intact and expanded

sips of water. The pharynx will then be anesthetized with Benzocaine 20% aerosol

- spray (Topex). After an interval of 5-10 min, the capsule sponge will be pulled out using steady traction using the string attached to the capsule sponge. As detailed in another Mayo IRB approved protocol (IRB 11-006429). The sponge will then be placed in a preservative solution and transferred to the laboratory for storage and subsequent analysis.
- b. Following completion of the capsule sponge study participants will fill out a tolerability questionnaire which allows patients to grade of discomfort during the procedure on a Likert scale of 0-10. 10 representing the "worst experience" and 0 the "best experience." This scale allows a comprehensive and individual assessment of the degree of pain, choking, gagging, and anxiety experienced during the procedure. Participants will also be asked if they would have the procedure again (yes/no).

C. Endoscopic assessment:

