A factorial design will be used to compare porosity of sponge 25 mm 10 pores per inch (PPI) vs. 25 mm 20 PPI, and Barrett's Esophagus vs. normal esophagus. Tolerability will be measured using a tolerability score as well as level of mucosal abrasion (scale 0-6, 6=worst). The assumed standard deviation for the tolerability score of 2.2 was obtained from Sami, et al.. Using a two-sided test of significance of 5% and 80% power, we can detect a minimal shift in tolerability score of at least 2. For mucosal abrasion score, a rough estimate of 1 standard deviation (s.d. ≈ range of data / 4) will be used and assuming a two-sided test of significance of 5% we have 86% power to detect a difference in mean mucosal abrasion score of at least 1. DNA yield will be measured using wild type Beta-actin. Using a two-sided test of significance of 5% we have 82% power to detect a fold change difference of 50%. All above power calculations are based on detection of main effect comparisons with n=20 per group. The ability to detect interactions between main effects will be very limited with the given sample size. Recruitment will continue until 40 individuals have successfully completed the sponge procedure using the

25 mm sponge. We anticipate 25% will decline swallowing sponges after they have consented, therefore the total number of people we anticipate recruiting will be set at 60.

Phase 2: For the detection of Barrett's Esophagus, sample size justification will be based on minimizing the width of the 95% confidence interval of the sensitivity for detecting Barrett's Esophagus with a fixed specificity of 90%. From table 2 below, based on various assumed sensitivities, the largest confidence interval width for the proposed sample size is less than ±9%. Similarly for detection of dysplasia among Barrett's Esophagus patients, the largest width for the proposed sample size is less than ±12. These confidence widths are reasonable for this initial feasibility study. We also intend to perform multivariable modeling using machine learning techniques to evaluate a minimum of 14 methylation markers. Using the rule of thumb for machine learning of 10-15 events per marker, a minimum of 140 to 210 cases and an equal number of controls is required (total 280 to 420 patients) to account for assay failures and indeterminate histological findings on endoscopic exam. We anticipate enrolling up to 1000 participants.

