In addition, clinically archived FFPE tissue from up to 10 cases will be used to assess methylated DNA marker levels in biopsies versus the sponge.

Due to the known dysplasia miss rate with routine surveillance endoscopy, we hypothesize that there will be undetected or missed dysplasia in BE patients with a negative surveillance histology. This imperfection in the endoscopic "gold" standard will bias the resulting accuracy estimates of methylation markers in a multitude of ways. There are several approaches in the literature to address this issue; all with their own caveats. The three approaches that will be investigated are latent class analysis, Bayesian estimation, and discrepant resolution. We have hence inflated the sample size estimates in table 2 to correspond with a 30% prevalence of undetected dysplasia in those with no dysplasia on conventional surveillance endoscopy to ensure that we have 50 true BE subjects without dysplasia.

Table 2

	BE vs. No BE			BE no dysplasia vs. BE w/dysplasia				
Confidence Level	0.95	0.95	0.95	0.95	0.95	0.95	0.95	0.95
Sensitivity	0.75	0.80	0.85	0.90	0.75	0.80	0.85	0.90
Confidence bands	0.085	0.078	0.070	0.059	0.105	0.097	0.087	0.073
N no BE/BE without dys/BE with dys	100	100	100	100	65	65	65	65

Statistical analysis

Phase 1: Tolerability score and level of mucosal abrasion will be summarized as median and interquartile range. Analysis of variance will be used to detect statistically significant differences in tolerability score and level of mucosal abrasion between different levels of sponge porosity and size. Failure/complication rate will be summarized as the percentage of the group total. Comparisons between sponge porosity and size for failure/complication rate will be analyzed using the Chi-squared test.

Phase 1 and 2: Marker specificity will be defined as the 90th percentile value in subjects without BE. Several markers will be combined based on the coefficients from a logistic regression model using subjects with BE vs subjects without BE as the response. This approach is used as they represent the broadest spectrum of disease and any marker combination that fails to discriminate between these two subgroups would not be of future value. The specificity of the combined markers will then be set equal to the 90th percentile in non-BE subjects. The corresponding sensitivity of individual markers as well as combined markers will be estimated with 95% confidence intervals.

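### The Phase 1 ANOVA names sponge size, which no longer varies, and omits Barrett's status, the second factor of the factorial; adding it is a free improvement

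*Combined protocol and SAP*

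**What the plan says.** The Phase 1 part of the section Sample size and Statistical analysis sets out the design: "A factorial design will be used to compare porosity of sponge 25 mm 10 pores per inch (PPI) vs. 25 mm 20 PPI, and Barrett's". The second factor is thus Barrett's against normal esophagus. It then gives the basis of the power figures: "All above power calculations are based on detection of main effect comparisons with n=20 per group". For tolerability, "Using a two-sided test of significance of 5% and 80% power, we can detect a minimal shift in tolerability score of at least 2", with an SD of 2.2. For abrasion it claims 86% power for a difference of 1, with an SD of 1. For DNA yield (beta-actin) it claims 82% power for a 50% fold change and gives no SD.

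Study procedures, part B, confirms that only porosity is randomised: "For phase 1 subjects will be randomized using concealed allocation to one of two capsule sponges: 25 mm 10 ppi, 25 mm 20 ppi". It does not mention stratification by Barrett's status. Table 1 in the sample size section has equal Barrett's and non-Barrett's counts under each sponge, but still shows four sponges, including the 30 mm size.

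The Phase 1 paragraph under Statistical analysis reads: "Analysis of variance will be used to detect statistically significant differences in tolerability score and level of mucosal abrasion between different levels of sponge porosity", with size as the other factor. The next test uses the same pair: "Comparisons between sponge porosity and size for failure/complication rate will be analyzed using the Chi-squared test". Neither sentence mentions Barrett's status, and no Phase 1 test is named for DNA yield.

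**The concern.** The named analysis lists a factor that cannot vary and leaves out one that does. Read literally, with one sponge size, the ANOVA is a one-way comparison of porosity, and any difference between Barrett's and normal patients goes into the error term. No section tests tolerability, abrasion or DNA yield by Barrett's status, although the power statement refers to main effects in the plural.

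At stake is the precision of the comparison that helps to choose the single sponge for all of Phase 2. Study Design bases that choice on acceptance, tolerability, mucosal irritation and DNA yield. If Barrett's status affects these outcomes, a model without it is less precise than the design allows. If allocation was not stratified, the unadjusted porosity difference also carries any chance imbalance in Barrett's patients.

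**Working it through.** **Inputs from the plan.** Two-sided 5%; n = 20 per sponge; tolerability shift δ = 2 with SD 2.2; abrasion difference δ = 1 with SD 1 (taken as stated).

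**Assumptions.** 10 patients per cell, normal outcomes with equal variance, no interaction. The documents do not give the Barrett's difference b. The range used is 0 to 3 points for tolerability and 0 to 1 point for abrasion. They also do not say whether the SDs are within-stratum or total, so both readings are shown.

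**Step 1: the plan's own figures.** For a two-group t-test, the noncentrality is δ / (SD × √(2/20)) on 38 df.
- Tolerability: 2 / (2.2 × 0.3162) = 2.87, power 80.0% (plan: 80%).
- Abrasion: 1 / (1 × 0.3162) = 3.16, power 86.9% (plan: 86%).

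Both reproduce approximately, with no Barrett's term in the model.

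**Step 2: SDs read as within-stratum.**
- With Barrett's status as an additive term, the noncentrality is unchanged and error df fall from 38 to 37.
- Without it, the porosity estimate is the same in balanced cells, but the expected error variance becomes SD² + 10b²/38. For tolerability with b = 2: 4.84 + 40/38 = 5.89, an SD of 2.43.
- Power without the term follows by integrating over the error variance: 38 × s²/SD² is noncentral chi-squared with 38 df and noncentrality 10b²/SD².

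| Outcome | b | Without Barrett's | With Barrett's |
|---|---|---|---|
| Tolerability | 0 | 80.0% | 79.9% |
| Tolerability | 1 | 78.5% | 79.9% |
| Tolerability | 2 | 73.7% | 79.9% |
| Tolerability | 3 | 65.7% | 79.9% |
| Abrasion | 0 | 86.9% | 86.8% |
| Abrasion | 0.5 | 85.5% | 86.8% |
| Abrasion | 1 | 80.9% | 86.8% |

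Simulation with 100,000 runs per setting agrees to within 0.2 point.

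**Step 3: SDs read as total.** The within-stratum SD is then √(SD² − b²/4). For tolerability with b = 2: √(4.84 − 1) = 1.96.
- Tolerability, b = 1: 80.5% without the term, 82.0% with it.
- Tolerability, b = 2: 82.3% without, 88.2% with.
- Abrasion, b = 1: 89.8% without, 94.5% with.

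**Step 4: if allocation is not stratified.** With 20 Barrett's patients among 40 and 20 per sponge, the hypergeometric chance of a 12 vs 8 split or worse, in either direction, is 34%. A 12 vs 8 split moves the unadjusted porosity difference by (12/20 − 8/20) × b = 0.2b. At an assumed b = 2 that is 0.4 points, against a standard error of 2.2 × √(2/20) = 0.70.

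**Step 5: cost when b = 0.** Tolerability power falls from 79.997% to 79.941%, and abrasion power from 86.895% to 86.848%. Each is under 0.1 point.

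**The case against.** The strongest reply is that nothing in the plan's power statement fails. The 80% and 86% come from a test without a Barrett's term, so they match the named analysis. The documents give no Barrett's effect on tolerability or abrasion, and the 2-point shift is a minimum detectable difference, not evidence that Barrett's patients differ by that much. The Phase 1 aims compare the two porosities only. The word size looks like a remnant of the four-sponge layout, and the ANOVA sentence may name the contrasts of interest rather than a full model.

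All of this stands, and it rules out several stronger readings that a reader might infer:
- **That the porosity comparison loses power outright.** It does so only if Barrett's status shifts the outcome, and it falls below the stated power only if the SDs are within-stratum.
- **That the porosity estimate is biased.** In balanced cells it is identical with or without the term. Under unstratified randomisation it is unbiased on average.
- **That type I error is a separate problem.** In balanced cells the test becomes conservative through the same inflated error variance. With unstratified allocation, type I error stays near 5% (4.8% in a simulation with a 2-point effect).
- **That failure and complication rates need a stratified exact test.** No gain has been shown for one in about 40 patients.

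What remains is the mismatch. Even as a remnant, the sentence leaves a design factor out of the analysis, and no other section puts it back.

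**Conclusion.** The point holds as a minor one: the Phase 1 analysis text does not match the factorial it is meant to analyse. The stated power is not wrong, and no bias is shown.

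The size of the cost depends on an unknown Barrett's effect. It is about 1.5 points of power for a modest effect (1 tolerability point or 0.5 abrasion point). Where the Barrett's effect equals the sized porosity difference, including the term gains about 6 points for tolerability under either reading of the SD, and about 5 to 6 for abrasion. These figures assume 10 per cell, which Table 1 suggests only through its old layout. Unstratified allocation would add a realistic chance of a modest shift in the unadjusted difference, which the same term corrects.

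It would go too far to say that a powered hypothesis is left untested. The sample size text implies a Barrett's main effect, but no Phase 1 aim asks for one on these outcomes. The sponsor should say which is meant. Since the term gains power or costs almost nothing in every case examined, this is a free improvement.

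**What to change.** In the Phase 1 paragraph under Statistical analysis:

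1. Replace porosity and size in the ANOVA with sponge porosity and Barrett's status as additive main effects. No interaction term is needed, since the plan already says interactions could hardly be detected. Report the adjusted porosity difference with its 95% CI.
2. Apply the same model to log beta-actin. DNA yield is a sponge-selection criterion with an 82% power claim but no named Phase 1 test.
3. State whether Barrett's vs normal is a hypothesis or only an adjustment factor.

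This takes a few sentences and one error degree of freedom (38 to 37). It needs no extra patients or visits, because Barrett's status is already established at the study endoscopy and beta-actin is already to be measured.

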Recently a sponge on a string device has been studied in BE screening.(19) This device consists of a polyurethane foam sponge compressed in a vegetable material derived capsule, attached to a string. The capsule is swallowed by the patient. The shell of the capsule dissolves in the gastric fluid releasing the foam device as a sphere which is then pulled out with the attached string, providing brushing/cytology samples of the proximal stomach and esophagus. Biomarker studies can then be performed on these samples to detect BE. Two large multicenter studies have been performed in the United Kingdom with such a device using trefoil factor 3 (a protein specific to BE epithelium) detected on immunohistochemistry as a BE marker, demonstrating the feasibility, safety and accuracy of this approach. (19, 20) The sensitivity and specificity of this marker in the detection of BE has been reported to be 73% and 94% for BE segments of > 1 cm in circumferential length. Additionally this capsule sponge device has been used safely in a study conducted at Mayo Clinic Rochester in subjects with eosinophilic esophagitis.(21)

Methylated DNA markers specific to BE epithelium (with and without dysplasia) have been described by us and others.(22) We have identified several methylated DNA markers which are highly specific and sensitive for the detection of BE and BE related dysplasia/carcinoma (see preliminary data section).

An investigational capsule sponge device (SOS: EsophaCap) is currently available in the United States in two sizes (25 mm and 30 mm size) and two porosity configurations (10 pores per inch [ppi] and 20 pores per inch). There is currently no data on the optimal size and pore configuration in terms of DNA yield, patient tolerability and safety on this device.

The aims of our Phase 1 pilot study are:

- 1. Compare patient acceptance and tolerability with the 25 mm 10 ppi and 25 mm 20 ppi configurations capsule sponge devices.
- 2. Compare presence and degree of mucosal abrasions following swallowing and withdrawal of capsule sponge, as determined on endoscopy with the 25 mm 10 ppi and 25 mm 20 ppi configurations) capsule sponge devices
- 3. Compare DNA yield obtained from esophageal cytology specimens obtained with the 25 mm 10 ppi and 25 mm 20 ppi and capsule sponge devices.
- 4. Explore sensitivity and specificity of DNA methylation markers in detecting BE and BE related dysplasia.

Phase 2 Aims:

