- x. If the visit 2 research procedure coincides with a participants clinically indicated upper EGD and procedures that are ordered cannot be done on the Clinical Research Unit, (i.e. radiofrequency ablation, endoscopic mucosal resection, esophageal dilation, endoscopic ultrasound) the research portion of the procedure will be done during the clinically indicated upper endoscopy. These research procedures will include the sponge on a string procedure, esophageal brushings, and surveillance biopsies (all paid for by research) as stated above.
- D. Post procedure assessment.
 - a. Patients will be called by the research coordinator at 7 days following the study (capsule sponge and endoscopy) to assess for any complications or adverse effects including bleeding, pain, dysphagia, need for seeking medical care and loss of work.

Assessment of Safety:

The Principal Investigator will monitor all adverse events and serious adverse events and they will be reported in IRB continuing reviews or immediately as appropriate. All complications and the endoscopy complication score will be reviewed every month by the PIs and continuation of the study will be assessed on this basis.

Biomarker assays:

a. Methylated DNA marker assessment:

Following histologic confirmation, tissue DNA will be extracted in usual fashion and bisulfite-treated. Methylation on target genes shown in our previous study to have >150-fold higher tissue levels in Barrett's Esophagus compared to esophageal squamous mucosa (*BMP3*, *NDGR4*, *TFPI2*, and *HPP1*) will then be quantified in blinded fashion by methylation-specific PCR. Novel markers for BE-related dysplasia and cancer identified by whole methylome sequencing will be quantified in blinded fashion on DNA extracted from cytologic brushings using bisulfite treatment and assay methods we have described previously. (23)

b. Levels of circulating biomarkers: Serum levels of Leptin, cytokines: IL6, 8, 10, 12p7,and methylated DNA markers will be measured. Assays will be performed using commercially available enzyme immunoassay kits. Unutilized samples will be stored for subsequent biomarker analysis.

Sample size and Statistical analysis:

Phase1: Detect ideal size and porosity for tolerability and DNA yield

Table 1

Sponge Diameter	25r	nm	30mm		
Pores Per Inch	10	20	10	20	
BE	5	5	5	5	
No BE	5	5	5	5	

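### The Phase 1 analysis tests sponge size, which is fixed at 25 mm, and leaves out BE status, the second factor of the stated factorial design.

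*Combined protocol and SAP*

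**What the plan says.** **Design.** The first Phase 1 aim is "Compare patient acceptance and tolerability with the 25 mm 10 ppi and 25 mm 20 ppi configurations capsule sponge devices", and the aims on abrasion and DNA yield have the same two arms. Under Capsule sponge assessment, Phase 1 subjects are "randomized using concealed allocation to one of two capsule sponges: 25 mm 10 ppi, 25 mm 20 ppi". That section leaves only porosity to be settled by Phase 1 for use in Phase 2. The Phase 1 sample-size text states: "A factorial design will be used to compare porosity of sponge 25 mm 10 pores per inch (PPI) vs. 25 mm 20 PPI". The same sentence then gives BE status as the other factor, in the words "and Barrett's Esophagus vs. normal esophagus". It adds "All above power calculations are based on detection of main effect comparisons with n=20 per group" and continues recruitment until 40 people have completed the procedure with the 25 mm sponge.

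**Analysis.** The Phase 1 paragraph under Statistical analysis applies ANOVA to the tolerability score and "level of mucosal abrasion between different levels of sponge porosity and size". For failures and complications it says "Comparisons between sponge porosity and size for failure/complication rate will be analyzed using the Chi-squared test". BE status appears in neither sentence. Later paragraphs use it only for marker accuracy and for the risk-factor models.

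**Table 1.** The Phase 1 sample-size heading reads "Detect ideal size and porosity for tolerability and DNA yield". Table 1 beneath it crosses 25 and 30 mm with 10 and 20 ppi and with BE and no BE, at 5 per cell.

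**The concern.** The analysis names one factor that does not vary and omits one that the design was built on. A size comparison cannot be carried out when every participant swallows a 25 mm sponge. BE status is half of the factorial, and power is quoted for main effects in the plural, yet no Phase 1 comparison of tolerability, abrasion or failure rate uses it.

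Two things are at stake. First, an analysis that cannot be run as written leaves the analyst to choose the model, possibly after seeing the data, and Phase 1 selects the sponge for a Phase 2 of up to 1000 participants. Second, if scores differ between people with and without BE, that difference goes into the error term of the porosity comparison when BE status is left out.

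**Working it through.** **Inputs (Phase 1 sample-size text).** Two-sided 5% test; n = 20 per main-effect group; tolerability shift 2, SD 2.2; abrasion difference 1, SD 1; 40 completers, all at 25 mm. An equal split by BE status (10 per cell) is assumed.

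**1. The plan's own power.** For a two-sample t test the noncentrality is δ / (σ√(2/n)), and √(2/20) = 0.3162.
- Tolerability: 2 / (2.2 × 0.3162) = 2.875. With 38 df (critical value 2.024), power is 80.0%, against 80% stated.
- Abrasion: 1 / (1 × 0.3162) = 3.162. Power is 86.9%, against 86% stated.

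Both are reproduced. Neither depends on a size term.

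**2. Can the written model be fitted?** With intercept, size and porosity and all 40 people at 25 mm, the size column is constant. The design matrix has rank 2 of 3, so the size effect cannot be estimated; the porosity effect can. With intercept, porosity and BE status the rank is 3 of 3.

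**3. Cost of adding BE status if it has no effect.** Residual df fall from 38 to 40 − 3 = 37 (critical value 2.026). Power is 79.9% for tolerability and 86.8% for abrasion.

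**4. Cost of omitting BE status if it has an effect.** Let g be the difference in mean tolerability between BE and no BE. The documents give no value, so g = 0 to 3 is an assumption, as is reading 2.2 as the SD within BE groups. With an equal split, leaving BE out raises the variance to 2.2² + g²/4.

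| g | Variance | SD | Noncentrality | Power without BE | Power with BE |
|---|---|---|---|---|---|
| 0 | 4.84 | 2.20 | 2.87 | 80% | 80% |
| 1 | 5.09 | 2.26 | 2.80 | 78% | 80% |
| 2 | 5.84 | 2.42 | 2.62 | 72% | 80% |
| 3 | 7.09 | 2.66 | 2.38 | 64% | 80% |

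Replacing g²/4 by 10g²/38, the expected rise in the residual mean square on 38 df, gives 80%, 78%, 72% and 63%. Hence 63-64% in the last row.

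These figures let BE status add noise to the porosity difference as well as to its standard error. If the split is exactly 10 per cell, only the standard error is inflated: the difference keeps its true standard error of 2.2 × 0.3162 = 0.696, and residual SS / 4.84 is noncentral chi-squared with 38 df and noncentrality 10g²/4.84. Simulating that case (400,000 draws) gives 80%, 79%, 74% and 66%, a slightly smaller loss.

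**5. Table 1.** Read whole, it has 2 × 2 × 2 = 8 cells of 5, or 40 people, with 4 × 5 = 20 at each porosity. The sample-size text also gives 40 people and 20 per porosity, but all at 25 mm. The totals agree; the layouts do not.

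**The case against.** The strongest reply is that this is leftover wording. The Phase 1 aims and the choice for Phase 2 concern porosity alone. Porosity is named in the ANOVA and can be tested, and software would drop a one-level size term. No aim asks about a BE main effect. If 2.2 is the total SD, with any BE difference already in it, omitting BE status still gives the planned 80%. All of this stands, and it limits the point to specification. It does not explain why a factor named in the sample-size text is absent from the analysis.

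Four stronger readings are tempting and are not supported:
- A reader might take the 25 mm half of Table 1, find 10 people per porosity, and infer that the stated power is lost. No design in the documents has that size. The whole table gives 20 against 20, and the sample-size text requires 40 completers at 25 mm.
- A reader might infer that randomisation is stratified by BE status. The documents call it a design factor but describe only concealed allocation to two sponges.
- A reader might infer that the text belongs to an older size-by-porosity design. No amendment log is shown. Table 1 itself contains BE rows, so the analysis omits BE status under either layout.
- A reader might claim a gain above the planned power from adding BE status. That needs an assumed share of variance that the documents do not give.

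Timing is a fair caution. Phase 2 follows completion of Phase 1, and enrolment at a site outside the Phase 1 location is described as closed, so the Phase 1 data may already have been analysed. That is an inference; other sections still treat the porosity choice as open.

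**Conclusion.** The point holds as a mismatch between design and analysis. One written comparison (size) cannot be estimated, and one named factor (BE status) is not analysed for tolerability, abrasion or failure rate. The porosity comparison survives, and with 20 per group power stays at about 80% and 87%.

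The harm from omitting BE status ranges from none, if scores do not differ by BE status, to a fall in tolerability power from 80% to about 63-64% for a 3-point difference. That range rests on an SD of 2.2 within BE groups, an equal split and assumed differences; exact balance makes the loss a little smaller. The text should be corrected because the remedy is cheap and settles the model in advance, not because the trial is too small.

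**What to change.** 1. For tolerability and abrasion, specify a two-way ANOVA with main effects for porosity and BE status.
2. Delete size from the ANOVA sentence, the chi-squared sentence and the Phase 1 sample-size heading.
3. Reconcile Table 1 with the sample-size text: 25 mm only, 40 completers, 20 per porosity, and 10 per cell if BE status is balanced. If balance is not guaranteed, say so.

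The cost is wording, a corrected table and one residual degree of freedom (tolerability power 79.9% instead of 80.0% if BE status has no effect). No extra participants or data are needed. If Phase 1 has already been analysed, the model with BE status should be reported as a post hoc clarification alongside the porosity comparison that was run.
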